180 glucose and insulin sensitivity (HOMA-IR), at 3, 6 and 12 months between the vagus nerve
181 cryoablation group and the lifestyle intervention monotherapy group.
182

183 The primary safety endpoint of the trial is occurrence of death and all procedure related
184 complications, such as bleeding, infection, pneumothorax, hemothorax, pulmonary injury,
185 complications of sedation, pain requiring hospital admission or treatment, dysphagia,
186 gastroparesis, nausea and vomiting, and gastrointestinal ulceration for the duration of the study.
187

188 Secondary outcomes include differences between treatment groups in any of the following
189 measures:

- 190 1. Body mass index (BMI), waist circumference, and waist-to-hip ratio at 3 and 6 months
191 compared to baseline
- 192 2. Lipids (total cholesterol, LDL, triglycerides) at 6 months compared to baseline
- 193 3. Systolic and diastolic blood pressure at 3 and 6 months compared to baseline
- 194 4. Daily caloric intake as measured by 3-day food recall compared to baseline at 3 and 6
195 months.
- 196 5. Changes in antihyperglycemic medication regimen compared to baseline at 3 and 6
197 months.
- 198 6. Appetite, hunger and satiety scoring by visual analog scale at baseline, 1 week, 1 month,
199 3 months and 6 months
- 200 7. Physical activity questionnaire (IPAQ) at baseline, 3 and 6 months
- 201 8. Fasting glucose and insulin levels at 3 and 6 months compared to baseline

202 203 **C. STUDY DESIGN:**

204 This is a randomized, controlled, unblinded clinical study in obese adult patients with T2D,
205 HbA1c 7.5-10.5%, BMI 30-40 kg/m² treated with non-insulin antidiabetic medications with

207 stable doses for at least 3 months.

208 Subjects will be pre-screened with the relevant questions from the Three Factor Food
209 Questionnaire by phone or in person to determine eligibility prior to consent. Following consent
210 and screening for trial eligibility, subjects will be randomized to treatment group. The primary
211 endpoint, glycemic control, will be assessed at 6 months post-procedure. Patients will be
212 recruited from the diabetes clinic at Grady Memorial Hospital and Emory University Clinics.
213

[figure not shown]
214 We will be screen up to 40 participants to be able to randomized 30 patients, they will be
215 enrolled in this pilot exploratory study. Patients will be randomly allocated to undergo either CT

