216 guided cryoablation of the vagus nerve plus lifestyle intervention or lifestyle intervention alone.

217 **Group 1:** CT guided cryoablation of the vagus nerve plus lifestyle intervention (n=15).

218 **Group 2:** Lifestyle intervention by trained RD/CDE (n=15).

219 All subjects will have the procedure performed at Grady Memorial Hospital or Emory University
220 Hospital Midtown or Johns Creek by trained study personnel.
221

222 The study schema is shown below. Both groups will undergo screening for eligibility followed
223 by randomization. If the subject is not fasting at time of initial consent and screening, he/she will
224 be brought back for a subsequent visit with fasting blood work. Subjects must be randomized
225 within 4 weeks of the screening visit. If the randomization visit falls outside of the 4 week time
226 frame, the subject must undergo repeat screening procedures. In- person lifestyle counseling will
227 be provided at baseline visit for both groups. Those undergoing cryoablation will receive a phone
228 call 24 hour post-procedure to evaluate for any immediate complications, 1 week in person
229 follow up visit, as well as a safety call at 2 months. Subjects in both groups will have weekly
230 contact with RD and in person follow up visits at 4 weeks, 3 months, and 6 months. Blood work,
231 anthropometric data and questionnaires will be administered at baseline, 3 months, and 6 months.
232 Safety follow up appointments will be scheduled at 9 months and 12 months, though no further
233 lifestyle counseling will be provided after 6 months. Questioning regarding adverse events and
234 side effects will occur at all visits, as well as assessment of glycemic control. Anti-
235 hyperglycemic medications will be adjusted at visits under the direction of the endocrinologist,
236 or as needed for clinically significant hypo- or hyperglycemic events.

237
238

239 Blood work will be as follows: For all lab parameters, subject results must be within the
240 reference range unless otherwise specified by inclusion/exclusion criteria or if assessed by study
241 physician to be not clinically significant.

Lab test	Baseline	3 months	6 months	9 months	12 months
Complete metabolic panel	X	X	X	X	X
Pregnancy test	X	X	X	X	
HbA1c	X	X	X	X	X
Lipid panel	X		X		
Insulin level	X	X	X		X
TSH	X				

242
243

D. STUDY PROCEDURE:

244 **Cryoablation procedure (to be performed by [name] or [name]):** Subjects will

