245 be NPO for 12 hours prior to the ablation procedure. Metformin and sulfonylureas will be held
246 the evening prior to the procedure. Subjects will present to the Interventional Radiology pre-
247 procedure holding area at 8:00 AM on the morning of the procedure and will have a peripheral
248 IV placed by nursing staff. Point of care blood glucose level will be checked; the procedure will
249 be deferred for BG >250 mg/dl until diabetes control can be better optimized. Low doses of
250 sedation will be used with IV versed and fentanyl. An Interventional Radiology nurse will
251 monitor the subject while sedation is being administered. Skin will be numbed using lidocaine.
252 The procedure will be done under CT guidance and involves a 4-5 mm scalpel incision followed
253 by percutaneous probe placement about the posterior gastroesophageal junction (the location of
254 the posterior vagal trunk). The probe will create a zone of decreased temperature (-20 to -40°C)
255 involving the posterior vagal nerve fibers/plexus. The cryoablation process will include a 3-

256 minute freeze, followed by a 1-minute thaw, and a second 3-minute freeze and 1 minute thaw.
257 After the procedure, a sterile dressing will be applied, and subjects will be monitored for 12
258 hours.

259

260 **Lifestyle Intervention:** All subjects will receive standardized dietary and exercise counseling
261 from a registered dietitian and exercise physiologist ([name]). Participants will be counseled
262 to follow a low carbohydrate diet providing a moderate amount of carbohydrates per day (~100
263 g). Focus will be on increasing fruits and vegetables and decreasing refined sugars and processed
264 foods. Dietary counseling will include motivational interviewing, goal setting and nutrition
265 education.⁴⁴ Subjects will also be encouraged to slowly increase physical activity to at least 150
266 minutes weekly. The lifestyle intervention structure will include detailed counseling sessions at
267 baseline, 3 and 6 months. These sessions ideally will occur face-to-face, although telemedicine
268 visit (via zoom) will be permitted on case-by-case basis due to the COVID-19 pandemic. In
269 addition, there will be weekly phone calls or texts (participants' choice) providing a total of 26
270 points of contact recommended by the USPSTF (United States Preventive Services Task
271 Force).⁴⁵

272

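### The primary HbA1c is timed from the procedure, which controls do not have, so delayed cryoablation patients are measured later after randomization than controls

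*Combined protocol and SAP*

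**What the plan says.** Section III.C (Study Design) states that the primary "endpoint, glycemic control, will be assessed at 6 months post-procedure". Group 2, with 15 patients, receives lifestyle intervention alone. The same section gives both groups weekly "contact with RD and in person follow up visits at 4 weeks, 3 months, and 6 months", without saying what those times are counted from. Its laboratory table has one baseline column and columns at 3, 6, 9 and 12 months. Baseline is not dated against randomization or against the procedure.

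The only limit stated around entry runs from screening to randomization, which must fall "within 4 weeks of the screening visit. If the randomization visit falls outside of the 4 week time" frame, screening is repeated.

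Section III.D (Study Procedure) checks glucose on the morning of the procedure, which will "be deferred for BG >250 mg/dl until diabetes control can be better optimized". It gives no maximum deferral and no rule on repeating the baseline HbA1c.

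Section III.G (Statistical Considerations) compares the 6-month change in HbA1c by a Wilcoxon or two-sample t-test. It names no time zero.

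**The concern.** The one sentence that anchors the primary time point uses a date that exists in one arm only. Controls can be counted only from randomization or from an undated baseline visit. Any gap between randomization and procedure, whether from scheduling or from a glucose deferral, then lengthens the interval from randomization to the primary HbA1c in the cryoablation arm alone.

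A scheduling gap might be unrelated to outcome. A glucose deferral is not: the patients delayed are those who were hyperglycemic on the day. So the unequal follow-up would fall on patients selected by a variable close to the endpoint, in an unblinded trial where an undefined anchor leaves visit timing to the site.

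**Working it through.** **The plan's own figure.** Section III.G assumes 15 per group and 20% attrition: 15 × 0.8 = 12 per group. It claims 80% power for a difference of 1.2 SD of the change. Alpha and sidedness are not stated; I assume 0.05 two-sided. For a t-test, the noncentrality is 1.2 × √(12/2) = 2.94 on 22 degrees of freedom, and power is 80.2%. The figure reproduces and is not affected by this point.

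**The time references side by side.**
- III.C, primary endpoint sentence: counted from the procedure.
- III.A, Objective 2: anthropometrics after intervention, which is not dated for controls.
- III.B, III.C visit list and laboratory table, III.G: months or weeks, with no origin.
- Screening to randomization: 4 weeks.
- Randomization to procedure: no limit in the visible text.

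Only the first of these states an anchor usable in the cryoablation arm, and none states one usable in both arms.

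**Consequence for follow-up time.** Take 6 months as 26 weeks. Interval from randomization to primary HbA1c = 26 + delay in Group 1, and 26 in controls counted from randomization. The delays are assumptions, because the documents give none.

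| Delay (weeks) | Group 1 (weeks) | Control (weeks) | Excess |
|---|---|---|---|
| 1 | 27 | 26 | 1/26 = 4% |
| 2 | 28 | 26 | 2/26 = 8% |
| 4 | 30 | 26 | 4/26 = 15% |
| 8 | 34 | 26 | 8/26 = 31% |

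**Consequence for the arm average.** Mean excess = (number delayed / 12) × delay, with 12 evaluable patients.
- 1 delayed by 1 week: 1/12 × 1 = 0.08 weeks.
- 2 delayed by 4 weeks: 2/12 × 4 = 0.67 weeks.
- 6 delayed by 8 weeks: 6/12 × 8 = 4 weeks.

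With few deferrals the arms differ little on average; the difference sits in the deferred patients.

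**Direction.** If baseline HbA1c is drawn before the deferral, any fall between randomization and procedure enters the Group 1 change, over a longer interval. If it is redrawn just before the procedure, that fall leaves the change score and the effect may be understated. The visible text does not say which applies.

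**The case against.** The strongest reply is that this is one loose phrase. Visits, laboratory columns and the statistical section read like a schedule shared by both arms, and the missing schema may show the anchor. A shared schedule may well be what is intended. But unanchored lists do not override the one sentence that states an anchor, and a clear schema would still have to be reconciled with it. (III.C also has a sentence on sites that, read literally, gives every subject the procedure. It conflicts with the definition of Group 2 and should be reconciled too.)

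Some mitigation stands. III.G will consider a model with visits as continuous time, medication changes are a secondary outcome, and this is a 30-patient exploratory pilot. None of this sets a time zero for the 6-month comparison.

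Four stronger readings are tempting, and the documents do not support them.
- A reader might multiply an assumed share deferred by an assumed HbA1c fall from optimization and call the product the bias. That measures treatment before the procedure, which a randomization clock leaves in place. It also assumes no comparable fall in hyperglycemic controls.
- A reader might infer that controls have no matching step. Anti-"hyperglycemic medications will be adjusted at visits under the direction of the endocrinologist" applies to both arms, as does the dose-adjustment trigger in III.E of a one-week average above 250 mg/dl. What is particular to Group 1 is the trigger, a single pre-procedure reading, and the delayed clock.
- A reader might infer that deferred patients get extra dietitian contact. III.D fixes the total at 26 for all, and III.C ends counseling at 6 months.
- A reader might conclude that randomization no longer protects the comparison. Allocation is untouched; the issue is visit timing, and co-treatment after randomization, in some patients.

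**Conclusion.** The point holds as a defect in the definition of the primary time point. Read literally, the plan gives delayed cryoablation patients a longer interval from randomization to the primary HbA1c than controls, and where the delay is a glucose deferral it is related to the outcome. The lack of a common time zero would need correcting even if no patient were deferred.

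The size in HbA1c points cannot be derived. The documents give no deferral rate, no delay and no date for baseline HbA1c. In time, assumed delays of 1 to 8 weeks add 4% to 31% to a delayed patient's interval; the effect on the arm comparison is small if few are delayed, and it can go either way. The conclusion rests on the visible text, since the schema could not be read.

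**What to change.** In III.C and III.G, define time zero as the date of randomization in both arms.
- Use the HbA1c at randomization, before any procedure, as baseline in both arms, including when the procedure is deferred.
- Count the 3-, 6-, 9- and 12-month efficacy visits from randomization.
- Keep the 24-hour, 1-week and 2-month contacts on the procedure clock, for safety.
- Record days from randomization to procedure and any medication change in that interval.
- Report a sensitivity analysis by time since procedure.

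The cost is a few lines of wording and two data items. The downside is that post-procedure exposure at the primary visit falls short of 6 months by the length of the delay: 26 − 4 = 22 weeks for a 4-week delay, and more for longer ones, since deferral has no stated maximum. The 9- and 12-month visits, which III.C describes as safety follow-up, shorten by the same amount.

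The change equalizes follow-up time only. Glycemic optimization before the procedure becomes part of the strategy as randomized, so medication changes should be described by arm. The deferral rule is a clinical matter and need not change for this purpose.

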21. History of autonomic dysfunction, including amyloidosis, Parkinson's disease, autoimmune disease, spinal cord injury

G. STATISTICAL CONSIDERATIONS:

464 The primary outcome is the difference in glycemic control (as measured by HbA1c) at 6 and 12
465 months between the vagus nerve cryoablation group and the lifestyle intervention group.
466 Summary statistics including mean, median, and standard deviations for the changes in HbA1c
467 at 3, 6, 9 and 12 months will be computed. We will then compare the changes at 6 months
468 between the two treatment groups by a nonparametric Wilcoxon test or a two-sample t-tests
469 (with appropriate data transformation if needed). We will conduct one-way ANOVA to estimate
470 the mean difference in glycemic parameters at 6 and 12 months month between the two
471 treatment groups. We may further adjust for some important confounders by using linear
472 regression models. We will also assess the glycemic control outcomes simultaneously across
473 different follow-up visits (i.e. 12, 24 weeks) through repeated measures ANOVA models, which
474 appropriately account for within-subject correlations in the measurements. In addition, we will
475 consider repeated measures linear regression model with visits incorporated as a continuous time
476 variable. We may include other covariates in the model when feasible.

477 The primary safety endpoint of the trial is the occurrence of death and all procedure related
478 complications, such as bleeding, infection, pneumothorax, hemothorax, pulmonary injury,
479 complications of sedation, pain requiring hospital admission or treatment, dysphagia,
480 gastroparesis, nausea and vomiting, and gastrointestinal ulceration for the duration of the study.
481 We will first use the Chi-square test (or Fisher's exact test) to compare the occurrence of this
482 primary safety endpoint between the two treatment groups. We will perform logistic regression
483 to evaluate the group difference while adjusting for other potential confounders such as age,
484 gender, and BMI. In addition, we will compare the number of procedure related complications
485 by using Poisson regression or Negative Binomial regression between the two treatment groups.
486 Standard model selection (e.g. forward, backward variable selection) and model checking
487 procedures (e.g. deviance residual plot and Hosmer- Lemeshow test) will be performed to ensure
488 the adequacy of the final models.

489

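### Three scheduled safety contacts exist only in the cryoablation arm, so the between-arm comparison of events that either arm can have is open to unequal detection, and controls have no stated route for the 1-week appetite scale

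*Combined protocol and SAP*

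**What the plan says.** **Safety contacts.** Section III.C (Study Design) limits three contacts to one arm: "Those undergoing cryoablation will receive a phone" "call 24 hour post-procedure to evaluate for any immediate complications, 1 week in person" "follow up visit, as well as a safety call at 2 months". Section III.E (Protection against risks) also times these contacts from the procedure.

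**Contacts in both arms.** Section III.C continues: "Subjects in both groups will have weekly" "contact with RD and in person follow up visits at 4 weeks, 3 months, and 6 months". It adds safety appointments at 9 and 12 months, not restricted by arm, and ties adverse event questioning to visits. Section III.D (Lifestyle Intervention) describes the weekly contact as counselling: "addition, there will be weekly phone calls or texts (participants' choice) providing a total of 26" points of contact. No adverse event questions or appetite scale are assigned to it.

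**Safety analysis.** The primary safety endpoint in III.B is death plus complications related to the procedure. Its list includes dysphagia, gastroparesis, nausea and vomiting, infection, and pain needing admission or treatment. Section III.G uses a Chi-square or Fisher test to compare the "primary safety endpoint between the two treatment groups. We will perform logistic regression" with covariate adjustment, and Poisson or negative binomial regression for complication counts. III.D states that the trial is unblinded.

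**Appetite.** Secondary outcome 6 in III.B, listed among differences between treatment groups, reads "Appetite, hunger and satiety scoring by visual analog scale at baseline, 1 week, 1 month" and continues to 3 and 6 months. III.D (Surveys) assigns the scale at 1 week to subjects in general. III.C lists questionnaires at baseline, 3 and 6 months only.

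**The concern.** When one arm is asked about symptoms more often, short-lived symptoms are more likely to be recorded in that arm even if they are equally common in both. Three of the five scheduled enquiries up to 3 months in the cryoablation arm have no counterpart in controls, and everyone knows the allocation. A between-arm test then mixes any true harm with a difference in how hard the trial looked. The direction is against cryoablation. Section III.G says the data will support planning of larger randomized studies, so a distorted rate could matter even where no test is significant.

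The appetite scale raises a related question. The 1-week score is a between-group outcome, but the plan does not say when, how or from which starting date a control supplies it.

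**Working it through.** **The plan's own figures.** The plan gives no detection rate and no safety power calculation. Its only power figure is 80% for a 1.2 SD difference in glycemic change with 12 per group. This reproduces (80.2%, t-test, two-sided 5% assumed) but has no bearing on this point.

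**Step 1: count scheduled safety enquiries (III.C).** Visits are counted because adverse events are asked about there. The two calls are counted because safety is their stated purpose.

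| | Cryoablation | Control |
|---|---|---|
| 24 hours | yes | no |
| 1 week | yes | no |
| 4 weeks | yes | yes |
| 2 months | yes | no |
| 3 months | yes | yes |
| 6, 9, 12 months | yes (3) | yes (3) |
| **Up to 3 months** | **5** | **2** |
| **Over 12 months** | **8** | **5** |

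Ratios: 8/5 = 1.6 over 12 months; 5/2 = 2.5 up to 3 months.

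**Step 2: illustrate what this could do.** Assume that true risk is equal, that each enquiry independently elicits a listed event with probability q, and that events count whatever their attribution. The proportion with any recorded event is 1 − (1 − q)^8 with cryoablation and 1 − (1 − q)^5 in controls. For q = 5%: 1 − 0.95^8 = 33.7% and 1 − 0.95^5 = 22.6%. Rejection rates are at a nominal two-sided 5% with 15 per arm. The count test compares Poisson totals with means 15 × 8 × q and 15 × 5 × q.

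| q (assumed) | Cryoablation | Control | Excess (points) | Fisher rejects | Fisher rejects, equal schedules | Count test rejects |
|---|---|---|---|---|---|---|
| 2% | 14.9% | 9.6% | 5.3 | 1.6% | 0.5% | 6.0% |
| 5% | 33.7% | 22.6% | 11.0 | 4.3% | 1.8% | 9.7% |
| 10% | 57.0% | 41.0% | 16.0 | 6.4% | 1.6% | 17.7% |
| 20% | 83.2% | 67.2% | 16.0 | 8.3% | 1.7% | 30.1% |

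Fisher's test rarely rejects at this sample size. The count comparison is more exposed.

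**Step 3: sort the endpoint components.**
- Possible in either arm, so open to unequal detection: nausea and vomiting, dysphagia, gastroparesis, infection, gastrointestinal ulceration, and pain needing treatment.
- Possible only with a procedure: sedation complications, incision bleeding, probe-related pneumothorax. Controls score zero however often they are asked, so a between-arm test is uninformative.
- Death: recording should not depend on the extra contacts.

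**Step 4: set the appetite passages side by side.** III.B and III.D call for a 1-week score without restriction by arm. III.C gives controls no 1-week visit and omits 1 week from its questionnaire times. Controls do have a weekly call or text, but the scale is not assigned to it. They also have no procedure date from which to count a week. A control score is therefore expected but has no stated route. At 1, 3 and 6 months both arms have visits.

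**The case against.** The strongest objection is that the tested endpoint is procedure-related complications, not all adverse events. Controls have no procedure, so apart from death their count is near zero by definition, and asking them more often would not change that. This stands for purely procedural items. For the others the plan leaves a dilemma. If control events are not counted because they cannot be attributed to a procedure, the test is uninformative. If they are counted, detection is unequal. Section III.G plans the comparison without saying which applies.

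Second, III.E gives subjects study contact details, allows unscheduled assessment, and requires all adverse events to be documented whether related or not. Events can therefore be captured between visits in either arm. This also stands. A reader might infer from the 5-to-2 count that equal rates would look 2.5 times higher with cryoablation. The documents do not support that, because it requires events to be captured only near scheduled contacts.

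Third, a reader might infer that the 1-week appetite comparison has no control data by design. The plan does not say so: III.D asks subjects in general for the score, the weekly contact could carry it, and the study schema is not visible in the text reviewed and may specify it. Nor do the documents single out 1 week as the time when an effect would show; the pilot reported reduced appetite at all time points.

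Finally, the 24-hour call is ordinary procedure monitoring and this is a small pilot. Both are true, and they argue for a modest change rather than new visits.

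**Conclusion.** The point holds in a limited form. Scheduled safety enquiry is unequal (8 against 5 over 12 months, 5 against 2 up to 3 months), and the planned comparison makes no allowance for it. For listed events that either arm can have, this can overstate the excess with cryoablation. The 5 to 16 point range rests on assumed elicitation probabilities of 2% to 20%, equal true risk, independence between enquiries, and no reporting between contacts. It is an illustration, not an estimate, and reporting between visits would shrink it. It does not extend to death or to events that require a procedure.

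For appetite, the defect is a missing collection route and time zero for controls at one time point of one secondary outcome. Control values are at risk of being missing; they are not excluded by the plan. Overall, this is an inexpensive improvement that should be made.

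**What to change.** 1. At the weekly dietitian contacts nearest 1 week and 2 months, ask controls the same scripted adverse event questions that the cryoablation arm is asked, and collect the 1-week appetite scale. Reconcile the questionnaire times in III.C with III.B and III.D.
2. Define time zero for controls so that these contacts line up with contacts timed from the procedure. Randomization alone may not do this, because III.D allows the procedure to be deferred.
3. In III.G, base the between-arm comparison on all listed events regardless of attribution, captured at contacts common to both arms. With step 1 there are 7 such contacts per arm (1 and 4 weeks; 2, 3, 6, 9 and 12 months). Without it there are 5.
4. Report procedure-related complications, including those found at the 24-hour call, descriptively in the cryoablation arm. Early procedural harms then stay visible, and no day-1 control contact is needed.

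The cost is a short script, one appetite form and a few minutes of staff time per control, with no new visits. One imperfection remains: the 1-week enquiry is in person with cryoablation and by call or text in controls.
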